9 DRUG FORMULATION AND PROCUREMENT

9.1 Drug Name

Adenovirus/PSA (Ad/PSA)

9.2 Classification

Vaccine

9.3 Mode of Action

The adenovirus is a replication-deficient virus unable to produce virus progeny in the infected cells. The virus will infect cells in the location of the injection site, the PSA gene will produce the protein product which will be recognized as an antigen by the immune system and produce anti-PSA immune responses. Based upon our pre-clinical studies in an animal model of human prostate cancer, these responses, mainly the CD8+ CTL response, will cause the destruction of PSA-secreting prostate tumors.

9.4 Dose Specifics and Route of Administration

The route of injection, vehicles for the vaccine, and dose schedules have been outlined in Section 5.1 of this protocol.

9.5 Availability

Produced and provided by Molecular Medicine, LLC, San Diego, CA

9.6 Storage

The vaccine is stored in the UIHC's Pharmacy Department in a -70°C temperature-monitored and controlled access freezer. Only the Investigational Pharmacist will remove the vaccine from the freezer and enter the amount removed in a trial-specific log.

9.7 Injection Procedures & Observation

At the weekly meetings of the clinical trial team at which the eligibility of the patients is decided, orders for the initial vaccine injection will be written by clinician members of the team. Orders for the second and third vaccine injections will be written at the meetings as close to the date of the scheduled injections as possible. On the designated days of injections and immediately prior to vaccination, the Investigational Pharmacist will mix the Ad/PSA (10⁸ pfu or 4.4 x 10⁹ particles) with the Gelfoam powder (30 mg/ml). Each vial of the vaccine contains twice the volume needed for each injection. One half of the vial will contain the proper pfu and particles required for the vaccination. The injection material will be taken from the pharmacy in a 1 ml. syringe with 25 gauge needle and presented to staff in the Clinical Research Unit. Each patient will be injected with approximately 0.16 ml. of the vaccine/Gelfoam material subcutaneously in the thigh. The exact volume of the vaccination mixture (Ad/PSA in Gelfoam) is not as important as the exact number of pfu or particles and that is controlled by using the required volume from the dose vial. The empty syringe will be disposed of in a biohazard container.

Patients will remain in the CRU for two hours after each injection to be monitored for signs of adverse events.

9.8 Manufacturing

- 9.8.1 The PSA cDNA provided by [name], Mayo Clinic, Rochester, MN, was placed 3' to the CMV promoter in a shuttle vector containing Ad5 DNA. The sequence inserted was the pre-pro form of PSA described by Lundwall (71) that encodes 262 amino acids with a predicted molecular weight of 28.8 kDa. Using methods previously described (72), the shuttle vector and E1a-E1b deletion mutant Ad5 DNA were transfected into HEK 293 cells, and recombination between the DNA species was allowed to occur. The amplification and purification of Ad/PSA was performed by the University of Iowa Gene Transfer Vector Core as previously described (73). Ad/lacZ used as a control was also obtained from the Gene Transfer Vector Core and is previously described (74).
- 9.8.2 The Principal Investigator provided the Ad/PSA vaccine used for the pre-clinical studies to Molecular Medicine, LLC of San Diego, CA for the production of the clinical grade product. Information on the manufacturing of the GMP Vaccine by Molecular Medicine, LLC is found in the accompanying documents supplied by the company.

10 STATISTICAL CONSIDERATIONS

The ideal endpoint would be a clinical outcome that is of particular relevance to the patient such as increased time to tumor progression, increased time to death or reducing the proportion of death. This trial is using a surrogate endpoint as a substitute to the clinically meaningful outcome since the tumors cannot be accessed directly. The association between the surrogate and survival rate had not been clearly established by any phase I & II trial. The trial consists of using Ad/PSA vaccine administered in multiple injections to prostate cancer patients with hormone—refractory metastatic prostate cancer—with the goal to induce anti-PSA T cells responses. Three injections of equal dose are proposed. The previous phase I trial consisting of a single injection in men with hormone-refractory metastatic prostate cancer was able to induce anti-PSA T cells responses. The Phase I consisting of a single injection using dose escalation protocol of the vaccine in an aqueous or matrix delivery vehicle did not show any significant AE. Additional pre-clinical pharmacology /toxicology studies required by the FDA did not show any significant side effects using the three-injection schedule. The primary endpoint is the serum PSADT.

For efficacy purposes, we expect at least 50% of the patients to show 50% increase in PSADT. This proportion is judged clinically important and anything less than 30% can stop the trial for futility. The ideal design would be a two-stage design of Simon (1989) requiring 32 patients. After testing the research intervention on 12 patients, if 3 did not have a 50% increase in PSADT, the trial will be terminated. Otherwise, an additional 20 patients will be recruited for the trial. The expected sample size will be 19.73 and the probability of early termination, 0.72. If the research intervention is not effective, there is 0.1 probability of concluding that it is. If the research intervention is effective, there will be 0.2 probability of concluding that it is not. However, due to the complexity of the trial, we will not use Simon (1989) but a more conservative approach consisting of using 31 patients in a one-stage design at efficacy level and a two-stage design at toxicity level for stopping rules. By using a one-stage design at efficacy endpoint, we are making

the probability of early termination for efficacy purposes to be zero. Early termination will be based on toxicity only. The reason for this design is due to the nature of the research intervention and is explained below. Enrollment will not stop unless stopping rules based on toxicity are satisfied: "After the third vaccine dose is administered, toxicity will be evaluated 90 days into the trial"

Due to the nature of the research intervention, anti-tumor activity will be potentially delayed and the primary efficacy endpoint will be determined 18 to 20 months after initial patient accrual. Since we will be able to assess PSADT after nearly 20 months into the study, it will be unreasonable to stop the study due to unsatisfactory results prior to that point. This is the main reason why we will carry a one-stage design for the primary endpoint and a two-stage design for toxicity. Criteria for proceeding with enrollment into a subsequent stage prior to the two-year efficacy evaluation will be based on assessment of toxicity in the patient cohorts since this can be done as early as 90 days into the trial.

For toxicity purposes, we will test the null hypothesis that the toxicity level is less than 15% versus the alternative that it is greater than 35%. The trial will be stopped whenever the null hypothesis is rejected. We will conduct these tests in 2 different looks—one after an enrolment of 17 subjects and the second after 25 subjects are enrolled.

If 5 out of 17 show grade 3 vaccine-related toxicity or higher, the trial will stop (this will correspond to testing the toxicity hypotheses at level alpha=0.05 with a power 77%); otherwise, an additional 8 subjects will enter the trial. If 7 out of 25 show a grade 3 toxicity or if 2 out of 17 show a grade 4 toxicity or higher, the trial will stop (this will be equivalent to testing the toxicity hypotheses at level alpha =0.05 with a power 82%); otherwise we will proceed to full registration. The overall type I error for this test is 0.09. In addition, the trial will stop if any vaccine-related deaths occur. The determination of a death related to the vaccine will be made by the clinical trial team and an audit by the Data and Safety Monitoring Board.

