5. RESEARCH INTERVENTION PLAN

5.1 Administration Schedule

Ad/PSA

All patients will receive three injections of 0.16 ml. (0.125 ml. vaccine + 0.035 ml. Gelfoam) of the Ad/PSA subcutaneously in the right thigh unless patient condition precludes the use of that leg, in which case the left thigh will be used for all three injections. The dose of the vaccine, based upon our results from the Phase I trial, will be 1 x 108 pfu (4.4 x 109 particles) in the Gelfoam matrix. The Gelfoam comes in sterile patient-ready packages. The virus will be suspended in sterile saline and the Gelfoam powder added in a ratio of 30 mg of powder per ml. of virus suspension. Injections will be spaced apart by 30 days, such that each patient will receive the vaccine on days 1, 30, and 60. The use of the matrix has been shown in collaborative pre-clinical experiments to enhance infection of host cells by the virus. Results from the Phase I trial indicated that the injection of the vaccine in Gelfoam did not produce any adverse events greater than those produced by the vaccine in an aqueous suspension. The vaccine induced anti-PSA immune response in patients injected as an aqueous or Gelfoam vaccination. Injections will be carried out in the University of Iowa Clinical Research Unit (CRU). Each subject will be required to stay in the CRU for two hours and observed for early signs of toxicities.

5.2 5.2 Design and Stages

The ideal design would be a two-stage design of Simon (1989) requiring 32 patients. But due to the complexity of the trial, a more conservative approach consisting of using 32 patients in a one-stage design at efficacy level and a two looks at toxicity level as means of stopping rules will be carried out. By using a one-stage design at efficacy endpoint, we are making the probability of early termination for efficacy purposes to be zero. The reason for this design is due to the nature of the research intervention as outlined in section 10. Stopping design based on toxicity is as follow: one look after 17 subjects are treated and another look after 25 subjects are treated. If 5 out of 17 show vaccine-related grade 3 toxicity or higher, the trial will stop. Otherwise, an additional 8 subjects will enter the trial. If 7 out of 25 show grade 3 toxicity or higher, the trial will stop otherwise we will proceed to full registration of 32 patients to assess efficacy.

6. Adverse Events

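### Section 10's sample-size paragraph gives figures that its described Simon design does not have, and the one-stage design adopted has no derivation, no success cut-off and two sizes (31 and 32)

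*Combined protocol and SAP*

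**What the plan says.** Section 10 sets the efficacy target and the uninteresting rate in two clauses: "we expect at least 50% of the patients to show 50% increase in PSADT" and "anything less than 30% can stop the trial for futility". Sections 5.2 and 10 both then say "The ideal design would be a two-stage design of Simon (1989) requiring 32 patients".

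Section 10 describes that design. The first-stage rule is "After testing the research intervention on 12 patients, if 3 did not have a 50% increase in PSADT, the trial will be terminated"; otherwise 20 more patients are recruited. Its properties are given as "The expected sample size will be 19.73 and the probability of early termination, 0.72". The error rates follow: "If the research intervention is not effective, there is 0.1 probability of concluding that it is" and "If the research intervention is effective, there will be 0.2 probability of concluding that it is not". No final-stage cut-off is given.

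The same paragraph then sets the Simon design aside for a one-stage efficacy design, of 31 patients in section 10 and 32 in section 5.2. Neither section says how many responders would count as success. On stopping, section 10 adds "Early termination will be based on toxicity only".

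**The concern.** The first stage, the total, the expected size and the early-termination probability should all describe one design, and they do not fit together. The stop sentence is also worded in terms of patients who did not respond, which reverses the usual rule.

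This paragraph is the plan's only sample-size derivation and its only source of efficacy error rates. If its figures belong to some other design, the one-stage design that replaces it inherits a total and two error rates that nobody has shown to apply. Without a cut-off, the primary result (the number of patients with a 50% increase in PSADT) could be called positive or negative after the data are seen.

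**Working it through.** **Inputs, all from section 10.** Uninteresting rate p0 = 0.30; target rate p1 = 0.50; alpha = 0.10; beta = 0.20 (power 0.80); first stage n1 = 12 with boundary 3; 20 more patients, total n = 32. All tail probabilities are exact binomial.

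**Formulas.** With stopping boundary r1 (stop if responders ≤ r1):
- PET = P(X1 ≤ r1 | p0), X1 ~ Bin(n1, p0)
- EN = n1 + (1 − PET)(n − n1)
- alpha and power = P(continue and total responders > r), at p0 and p1

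**Step 1: do the stated figures agree with each other?** Put the stated PET into the stated stages: 12 + (1 − 0.72) × 20 = 17.6, not 19.73. Rounding in PET (0.715 to 0.725) moves this only between 17.7 and 17.5.

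**Step 2: reproduce the stated figures.** A search of two-stage designs meeting alpha ≤ 0.10 and power ≥ 0.80 gives, as the design with smallest expected size: stop if ≤ 5 of 15 respond, add 17, declare activity if > 12 of 32.
- PET = P(Bin(15, 0.3) ≤ 5) = 0.7216
- EN = 15 + (1 − 0.7216) × 17 = 15 + 4.73 = 19.73
- alpha 0.0997, power 0.804

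So 32, 19.73 and 0.72 all reproduce, with a first stage of 5/15.

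**Step 3: the rule as described**, read as stopping on 3 or fewer responders among 12.
- PET = 0.0138 + 0.0712 + 0.1678 + 0.2397 = 0.4925
- EN = 12 + (1 − 0.4925) × 20 = 12 + 10.15 = 22.15

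**Step 4: other readings of the 3**, all with 12 then 20.

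| Reading | PET | EN |
|---|---|---|
| Stop at ≤ 2 responders (fewer than 3) | 0.25 | 26.94 |
| Stop at ≤ 3 responders | 0.49 | 22.15 |
| Stop at ≤ 4 responders | 0.72 | 17.53 |
| Literal: stop at ≥ 3 non-responders (≤ 9 responders) | 0.9998 | 12.00 |
| Stated in the plan | 0.72 | 19.73 |

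No reading gives both stated values. Taken literally, the sentence would stop the trial with probability 0.98 at a true 50% rate.

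**Step 5: error rates of the described rule.** No final cut-off is stated, so these depend on what is assumed.
- Boundary ≤ 3: success above 12/32 gives alpha 0.118, power 0.853; above 13/32 gives 0.064 and 0.785. Neither meets both targets.
- Boundary ≤ 2: success above 13/32 gives alpha 0.0685, power 0.807. Both targets are met.

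**Step 6: the one-stage design actually adopted.** alpha = P(Bin(n, 0.3) ≥ k); power = P(Bin(n, 0.5) ≥ k).

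| n | Success if at least | alpha | power | Meets 0.10 and 0.80 |
|---|---|---|---|---|
| 31 | 13 | 0.107 | 0.859 | no |
| 31 | 14 | 0.053 | 0.763 | no |
| 32 | 13 | 0.133 | 0.892 | no |
| 32 | 14 | 0.069 | 0.811 | yes |
| 32 | 15 | 0.033 | 0.702 | no |

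The Simon final cut-off of more than 12 of 32 is the row with at least 13. Carried into the one-stage test, it exceeds the stated alpha.

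**The case against.** The strongest reply is that section 10 discards the Simon design in the same paragraph, and that enrolment stops only on the toxicity rules. That stands. A reader might infer that a wrong or reversed futility rule could halt the trial, or that the 0.98 stopping probability is a real risk. The documents do not support this, because that rule never operates.

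Three other inferences also go too far:
- **That none of the design's stated properties hold.** The total does: 12 + 20 = 32. The early-termination probability and expected size fail. The error rates cannot be declared wrong, because no final cut-off is stated.
- **That no cut-off could meet both error rates.** This is true if the boundary means 3 or fewer responders, but not if it means fewer than 3 (step 5). The sentence is too unclear to settle which.
- **That 32 patients is the wrong number.** It is valid for the stated inputs, both as the optimal Simon total and as a one-stage test.

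One can add that a 12-patient first stage with boundary 3 is the first stage of the minimum-total design for the same inputs (more than 11 of 28; PET 0.49, expected size 20.12), which suggests that two designs were merged. That is an inference about origin; the documents never mention 28.

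The reply does not reach the design that is used. The error rates belong only to the discarded design, and nothing takes their place.

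**Conclusion.** The point holds as a documentation error with one live consequence. The described two-stage rule, read as 3 or fewer responders, has early-termination probability 0.49 and expected size 22.15, against the stated 0.72 and 19.73, and no reading of the boundary recovers both. This changes no interim decision and no patient numbers.

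The live consequence is that the adopted one-stage efficacy test has no derivation, no success cut-off and two sizes. The choice between 31 and 32 matters: at 31 no cut-off keeps alpha at or below 0.10 with power of at least 0.80, while at 32 a cut-off of 14 does.

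This rests on p0 = 0.30 and p1 = 0.50 as the intended rates, on 0.1 and 0.2 as the intended error rates for the one-stage test, and on all 32 patients being counted in the denominator.

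The futility clause and the statement that early termination rests on toxicity alone also disagree as worded. The clause can be read as the null rate of the discarded design, so this is a matter for reconciliation rather than evidence of a hidden stopping rule. A reader might conclude that the clause should simply be deleted, but it is the only place the documents give the 30% null.

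**What to change.** In section 10:
1. Replace the Simon paragraph with the test that will be used: a one-stage exact binomial test of 30% versus 50%, N = 32, success if at least 14 of 32 patients have a 50% increase in PSADT (alpha 0.069, power 0.811). Make the matching change to the Simon sentence in section 5.2.
2. Change 31 to 32, to agree with section 5.2.
3. Do not bring over the Simon cut-off of more than 12 of 32; in a one-stage test its alpha is 0.133.
4. Keep 30% explicitly as the null (uninteresting) rate, and reconcile the clause about stopping for futility with the statement that early termination is based on toxicity only.

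The cost is protocol wording. No patients, visits or measurements are added, since section 5.2 already plans 32.

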- 4.5 No patient may be enrolled or begin research intervention prior to registration and assignment of a patient number. As a follow-up, University of Iowa Cancer Center will provide the investigator with written confirmation of each patient's registration.
- 4.6 All investigators will be notified by the Chair of the Protocol Review and Monitoring Committee or by the trial's Data and Safety Monitoring Board if the study is placed on administrative hold, and when the study is completed or closed to further patient enrollment.
- 4.7 Patients must begin the vaccine protocol within 30 days of registration (date the study committee approves patient eligibility).

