6.2 Procedures of documentation of AEs

All AEs occurring during the study must be documented, regardless of the assumption of a causal relationship, on the respective AE CRF. All events which occurred after signed informed consent should be documented. The investigator should ensure that all events are recorded that occurred within at least 4 weeks after the last exposure to the study drug (through Day 90).

Documentation of AEs includes: date of onset and offset, intensity, frequency, seriousness, related interventions and outcome. The investigator will also evaluate the probability of a causal relationship of the adverse event to the study medication as being: "definite, probable, possible, unlikely, or unrelated."

All unanticipated problems involving risk to subjects or others, serious adverse events related to participation in the study and subject deaths related to participation in the study will be promptly reported bν [contact]),bν email ([contact]), or by [contact]) to the USAMRMC, Office of Research Protections, Human Research Protection Office. A complete written report will follow the initial notification. In addition to the methods above, the complete report will be sent to the U.S. Army Medical Research and Materiel Command, ATTN: MCMR-ZB-PH, [name].

The medical monitor is required to review all unanticipated problems involving risk to volunteers or others, serious adverse events, and all volunteer deaths associated with the protocol and provide an unbiased written report of the event. At a minimum, the medical monitor should comment on the outcomes of the event or problem, and in the case of a serious adverse event or death, comment on the relationship to participation in the study. The medical monitor should also indicate whether he/she concurs with the details of the report provided by the study investigator. Reports for events determined by either the investigator or medical monitor to be possibly or definitely related to participation and reports of events resulting in death should be promptly forwarded to the HSRRB.

Expedited reporting

The investigator must immediately report serious adverse events (SAE) occurring or observed during the course of the study and within 4 weeks of last administration of the study drug to the FDA, IRB, OBA, and CRU.

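### Sections 5.2 and 10 conflict on when the toxicity boundaries act: whether accrual waits, what triggers a look and how much follow-up it needs are not settled

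*Combined protocol and SAP*

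**What the plan says.** Section 10 (Statistical Considerations) makes toxicity the only ground for early termination: "Enrollment will not stop unless stopping rules based on toxicity are satisfied". It continues: "After the third vaccine dose is administered, toxicity will be evaluated 90 days into the trial". It places the two looks "one after an enrolment of 17 subjects and the second after 25 subjects are enrolled".

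Section 5.2 (Design and Stages) places them differently: "one look after 17 subjects are treated and another look after 25 subjects are treated".

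Both sections set the first boundary at 5 of 17 with vaccine-related toxicity of grade 3 or higher, and both say that 8 more subjects enter if it is not met. Section 10 adds that moving to a subsequent stage depends on the toxicity assessment. The second boundary is 7 of 25. Section 10 alone adds a criterion of 2 of 17 with grade 4 or higher, and a stop for any vaccine-related death.

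Three timing facts bear on this. Injections are scheduled "such that each patient will receive the vaccine on days 1, 30, and 60" (section 5.1). Adverse events are recorded through day 90 (section 6.2). Section 4.7 says: "Patients must begin the vaccine protocol within 30 days of registration". Neither section 5.2 nor section 10 says that accrual pauses after patient 17 or 25, or how much follow-up those patients need before the boundary is applied. No accrual rate is given.

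**The concern.** A look defined by a patient count, with an outcome that takes 90 days to complete, needs two more rules: how much follow-up counts as complete, and what accrual does meanwhile. Without them the first look is either made early on partial data, or made late while further patients may be injected. The first weakens the boundary below its stated power. The second means that the boundary can act after some of the patients it is meant to protect have been exposed.

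There is also a point that does not depend on accrual. The rate boundaries are written only for fixed looks. If the fifth qualifying patient appears well before patient 17, the rule does not formally act until the look.

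**Working it through.** **Inputs from the documents.** Boundaries of 5 of 17 and 7 of 25, read as that many or more; toxicity rates of 15% (null) and 35% (alternative); evaluation at day 90; up to 30 days from registration to first injection. **Assumed:** accrual of 0.5 to 2.7 patients per month, evenly spaced, with injection at entry and 30.44 days per month.

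**1. The plan's own figures.** Exact binomial:
- P(X ≥ 5 | n = 17, p = 0.35) = 0.765, against a stated 77%.
- P(X ≥ 7 | n = 25, p = 0.35) = 0.827, against a stated 82%.

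The power figures reproduce, and they assume complete data on 17 and 25 patients. The error rates do not: at p = 0.15 the exact values are 0.099 and 0.070 (stated 0.05 each), and 0.120 overall (stated 0.09). That is a separate matter and is not relied on here.

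**2. Look made when patient 17 enrols.** Patient i has then been followed for (17 − i) × 30.44 / rate days, and day 90 is 89 days after day 1.
- 1 per month: 89 / 30.44 = 2.9, so the last 3 are incomplete and 14 of 17 are complete.
- 2 per month: 89 / 15.22 = 5.8, so the last 6 are incomplete and 11 are complete.

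Counting only complete patients at 35% toxicity, P(X ≥ 5) is 0.577 with 14 and 0.332 with 11. These are lower limits, because partly followed patients can also contribute events.

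**3. Look waits for patient 17's day 90, with accrual open.** Patients entering = rate × 90 / 30.44, capped at the cohort of 8.

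| Rate per month | Enter before the look |
|---|---|
| 0.5 | 1.5 |
| 1 | 3.0 |
| 2 | 5.9 |
| 2.7 | 8.0 |

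Half the cohort (4 of 8) requires 4 × 30.44 / 90 = 1.35 per month. If the clock starts at registration and injection follows 30 days later, the window is 120 days and the figures are 3.9 at 1 per month and 7.9 at 2 per month.

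**4. Accrual held until the look.** None enter.

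**5. Fixed look against running count.** Among trials with at least 5 of 17, the fifth affected patient is on average number 12.0 at 35% toxicity and 9.8 at 50%. If toxicity shows immediately, the boundary is decided 17 − 12.0 = 5.0 or 17 − 9.8 = 7.2 patients before the look. With event times spread evenly over 90 days (an assumption, simulated), the patients among the first 17 who would be spared are:

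| Rate per month | 35% toxicity | 50% toxicity |
|---|---|---|
| 1 | 4.0 | 6.3 |
| 2.7 | 2.2 | 3.9 |

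The probability of reaching 5 of 17 is the same either way: 0.099, 0.765 and 0.975 at 15%, 35% and 50%.

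**The case against.** The best defence is that the lead sentence concerns efficacy. It follows the statement that early termination for efficacy has probability zero, and the next paragraph explains why there is no futility stop. Read so, it does not address accrual during a pending toxicity look, and the gate for the next 8 subjects governs. The overrun is then zero and the stated power holds. This reading is reasonable. It still leaves the hold unstated, the required follow-up undefined and the trigger inconsistent between sections.

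A reader might infer that the plan plainly lets the second cohort be injected before the first boundary is applied. The documents do not support that, because the gate stands in section 10 as well as section 5.2. A reader might also infer that nothing can act before patient 17. That goes too far: a vaccine-related death stops the trial at any time, serious events reach the principal investigator within 24 hours (section 6.2), an administrative hold is foreseen (section 4.6), individual patients are held or removed for toxicity (section 8.5.1.1) and records are audited quarterly (section 8, data management). None of these, however, applies the grade 3 rate boundary early.

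Finally, fixed-count looks are an ordinary staged design, and running counts alone do not supply an accrual hold. Both points stand, so the fix has to settle the hold separately.

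**Conclusion.** The inconsistency is real and should be corrected. Sections 5.2 and 10 differ on the trigger, section 10 is at odds with itself on whether enrollment waits, and neither fixes the follow-up needed before a look.

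The size depends on a rate that the documents do not give. With accrual open, the overrun is about 3 of 8 at 1 per month and all 8 at about 2.7 per month; it is zero if accrual is held. To say that much of the second cohort would be exposed therefore needs both the open-accrual reading and at least about 1.35 patients per month. If the look is instead made at patient 17's enrolment, the 77% power is not assured.

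The gain from running counts is 5 to 7 patients only if toxicity is immediate. With events spread over 90 days it is about 4 to 6 at 1 per month and 2 to 4 at 2.7 per month, for toxicity of 35% to 50%.

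**What to change.** 1. Keep the existing thresholds but apply them as running counts: the stop acts as soon as the 5th patient with a qualifying vaccine-related event is recorded among the first 17 treated, or the 7th among the first 25 treated. Only the timing changes.
2. Use *treated* as the trigger in both sections.
3. Reconcile the sentence on enrollment not stopping with the gate. State whether accrual waits after patients 17 and 25, and what follow-up those patients need before a look counts as passed.
4. Reconcile the grade 4 criterion (2 of 17), which appears only in section 10, within its second-look sentence. Also state whether the second boundary counts vaccine-related events only, since neither section repeats that qualifier there.

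The cost is wording and continuous event tracking, plus a longer enrollment period if accrual is made to wait.

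### The toxicity stopping boundaries do not have the stated error rates: exact alpha is 0.099 and 0.070 rather than 0.05 at each look, and 0.12 rather than 0.09 overall

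*Combined protocol and SAP*

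**What the plan says.** The toxicity paragraphs of section 10 set out the hypotheses: "we will test the null hypothesis that the toxicity level is less than 15% versus the alternative that it is greater than 35" per cent. The test is one-sided and drives stopping: "The trial will be stopped whenever the null hypothesis is rejected". There are two looks, "one after an enrolment of 17 subjects and the second after 25 subjects are enrolled".

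- **First look.** "If 5 out of 17 show grade 3 vaccine-related toxicity or higher, the trial will stop"; of this rule the plan says "this will correspond to testing the toxicity hypotheses at level alpha=0.05 with a power 77" per cent. If the boundary is not reached, "otherwise, an additional 8 subjects will enter the trial".
- **Second look.** The trial stops at 7 of 25, or if 2 of 17 have toxicity of grade 4 or higher; "this will be equivalent to testing the toxicity hypotheses at level alpha =0.05 with a power 82" per cent.
- **Overall.** "The overall type I error for this test is 0.09". Any vaccine-related death also stops the trial.

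Section 5.2 repeats the 5 of 17 and 7 of 25 boundaries without error rates. Neither section names the method used to calculate alpha or power.

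**The concern.** With 17 patients and a 15% rate, 2.55 events are expected, so 5 or more is not rare enough for a 0.05 test. The stated figures also look inconsistent with one another: the powers appear to belong to one calculation and the alphas to another.

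Section 10 says that early termination rests on toxicity only, so this is the trial's one statistical stopping rule. The investigators, the monitoring board and the funder's oversight office would read a boundary crossing in the light of these error rates. If alpha is understated, they would take a crossing as stronger evidence of excess toxicity than it is, and would underrate the risk of halting a trial whose toxicity rate is no worse than the plan's own limit.

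**Working it through.** **Inputs, all from section 10.** Null rate 0.15, alternative 0.35, one-sided; looks at n = 17 and n = 25 (17 + 8); stop at 5 and at 7 cumulative events. Stated: alpha 0.05 and power 77%; alpha 0.05 and power 82%; overall type I error 0.09. I take the same event, vaccine-related toxicity of grade 3 or higher, to be counted at both looks.

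**Step 1: the stated powers.** With exact binomial tails,

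- P(X ≥ 5 | n = 17, p = 0.35) = 0.7652, stated as 77%;
- P(X ≥ 7 | n = 25, p = 0.35) = 0.8266, stated as 82% (a match if truncated; it rounds to 83%).

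The powers therefore reproduce when the rules are read as 5 or more and 7 or more.

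**Step 2: alpha for those boundaries.**

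- P(X ≥ 5 | 17, 0.15) = 0.0987, stated as 0.05;
- P(X ≥ 7 | 25, 0.15) = 0.0695, stated as 0.05. This treats the second look as a stand-alone test.

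**Step 3: overall error.** The trial stops at the first look, or passes it with x < 5 events and then has at least 7 − x among the next 8 patients:

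P(stop) = P(X17 ≥ 5) + Σ(x = 0 to 4) P(X17 = x) · P(X8 ≥ 7 − x).

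At p = 0.15:

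| x | P(X17 = x) | P(X8 ≥ 7 − x) | product |
|---|---|---|---|
| 0 | 0.0631 | 0.00001 | 0.0000 |
| 1 | 0.1893 | 0.0002 | 0.0000 |
| 2 | 0.2673 | 0.0029 | 0.0008 |
| 3 | 0.2359 | 0.0214 | 0.0050 |
| 4 | 0.1457 | 0.1052 | 0.0153 |

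The products sum to 0.0212, so the overall type I error is 0.0987 + 0.0212 = 0.1199, stated as 0.09. At p = 0.35 the same formula gives 0.7652 + 0.0990 = 0.8642.

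**Step 4: other readings.**

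| Reading | Alpha, look 1 / look 2 | Overall | Power, look 1 / look 2 |
|---|---|---|---|
| Stated | 0.05 / 0.05 | 0.09 | 77% / 82% |
| ≥5 and ≥7, exact | 0.099 / 0.070 | 0.120 | 76.5% / 82.7% |
| >5 and >7, exact | 0.032 / 0.025 | 0.043 | 58% / 69% |
| ≥5 and ≥7, normal, no continuity correction | 0.048 / 0.034 | 0.062 | 69% / 77% |
| ≥5 and ≥7, normal, continuity correction | 0.093 / 0.062 | 0.113 | 77% / 83% |

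Mixed boundaries give an overall error of 0.076 (6 of 17, 7 of 25) or 0.103 (5 of 17, 8 of 25). Mid-p alphas are 0.065 and 0.047; Poisson alphas are 0.116 and 0.086. Two independent looks at 0.05 would give 1 − 0.95² = 0.0975. None of the readings tried yields 0.05, 0.05 and 0.09 together with 77% and 82%.

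A possible origin is the uncorrected normal cut-off at one-sided 0.05:

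- 17 × 0.15 + 1.645 × √(17 × 0.15 × 0.85) = 4.97;
- 25 × 0.15 + 1.645 × √(25 × 0.15 × 0.85) = 6.69.

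These round up to 5 and 7. Since the plan names no method, this is only inference, and the finding does not depend on it.

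**Step 5: the grade 4 rule.** The plan gives no grade 4 rate, so one has to be assumed. Let g be the grade 4 rate within the 15%, so that each event is grade 4 with probability g/0.15. Adding a stop at two or more grade 4 events among the first 17 gives, by exact calculation:

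| Assumed g | 1% | 2% | 3% | 5% |
|---|---|---|---|---|
| Overall false-stop probability | 0.127 | 0.147 | 0.178 | 0.262 |

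The death rule can only add to these.

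**The case against.** The strongest reply concerns consequence. The null is a rate below 15%, and 0.099 and 0.120 apply at its edge. Inside it the false-stop probability drops quickly: at 12% it is 0.045 at the first look and 0.052 overall; at 10%, 0.022 and 0.025. Section 10 reports no significant adverse events in phase I, although with a single injection, so the true rate may lie well inside the null. The error also runs towards stopping too readily, the boundaries are counts that can be applied as written, and the PSADT analysis does not use these alphas.

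All of that stands as a limit on the practical harm. It does not rescue the figures, because type I error for a composite null is taken at its boundary. Nor does a lower null rate help: an alpha of 0.05 needs a rate of about 12.4% at the first look and about 13.9% at the second, so no single rate produces both.

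Two narrower objections also have force. The grade 4 scenarios rest wholly on assumed rates, and 5% would make one third of the qualifying events grade 4, which nothing in the plan supports; they show direction and no more. Secondly, the second-look wording omits the vaccine-related qualifier, and section 10 there also omits the words covering higher grades, so the 0.120 depends on the natural reading that one event definition serves both looks. The stand-alone alphas of 0.099 and 0.070 do not need that reading.

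**Conclusion.** The concern holds. At 15% true toxicity the exact false-stop probability is 0.099 at the first look, about twice the stated 0.05, and 0.070 for the second boundary taken alone; the second look adds 0.021 for patients who pass the first. Overall it is 0.120, one third above the stated 0.09 (0.120/0.09 = 1.33). The contradiction is visible without the two-look calculation, since the first look alone exceeds the stated total and a further look cannot reduce it. The stated powers are right to within rounding or truncation.

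The result assumes independent patients with a common event rate and, for the overall figure, one event definition at both looks. Because the grade 4 and death rules are not counted, 0.120 is a lower bound at 15%. This is a misstatement of operating characteristics that should be corrected; it does not threaten patient safety or the efficacy analysis.

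**What to change.** Keep the boundaries and replace the figures in section 10:

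- first look: alpha 0.099, power 0.765;
- second look taken alone: alpha 0.070, power 0.827;
- both looks: type I error 0.120, power 0.864.

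State that these are exact binomial values at 15% and 35%, and that they exclude the grade 4 and death rules; alternatively, give the overall error with the grade 4 rule under a stated grade 4 rate. Use the same event wording at both looks.

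The cost is a few replaced numbers and a sentence. The stated error rates become less favourable, and nothing changes in how the trial is run.

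If the sponsor instead wants alpha of at most 0.05 at each look, the boundaries would have to be 6 of 17 and 8 of 25. These have alpha 0.032 and 0.025, overall error 0.043, and power 58%, 69% and 73% overall. That would be a design change which gives up sensitivity to excess toxicity, and correcting the text does not require it.
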